Specify the funding source and/or cooperating organization(s) (e.g., National Cancer Institute, Ford Foundation, Eli Lilly & Company, South Western Oncology Group, Bureau of Prisons, etc.):

The laboratory (OrthoApnea® laboratory, Malaga, Spain) that produces the device (NOA SLEEP APNEA AND SNORING DEVICE) will provide the devices at no cost for the research team nor to the patient, along with a home sleep apnea test machine (Alice Nightone, Phillips). No direct economical contribution will be provided to the research team nor to the patients. This will be an independent study, with no participation of laboratory representatives.

Add Related Grants

If applicable, please search for and select the OSPA Account number or Electronic Internal Approval Form (eIAF) # (notif #) associated with this IRB application using the "Add Related Grants" button.

If required by your funding agency, upload your grant using the "Grant/Contract Attachments" button.

[Add Related Grants](#)

[Grant/Contract Attachments](#)

The research involves use of Department of Defense (DoD) funding, military personnel, DoD facilities, or other DoD resources. (See [DoD SOP](#) and [DoD Summary](#) for details)

Yes No

Using the "attachments" button (below), attach applicable materials addressing the specific processes described in the DoD SOP.

[DOD SOP Attachments](#)

Additional Certification: (If your project is federally funded, your funding agency may request an Assurance/ Certification/Declaration of Exemption form.) Check the following if needed:

Protection of Human Subjects Assurance/Certification/Declaration of Exemption (Formerly Optional Form – 310)

[Assurance/Certification Attachments](#)

OTHER REVIEW COMMITTEES

0 unresolved
comment(s)

If you check any of the below committees, additional materials may be required with your application submission.

Does your research fall under the purview of any of the other review committees listed below? [If yes, check all that apply and attach applicable materials using the attachment button at the bottom of your screen.]

Yes No

Additional Information	
 Institutional Biosafety Committee	
• Institutional Biosafety Committee (IBC) - Attach required IBC materials
 Radiation Safety Committee	
• Radiation Safety Committee (RSC) - For applicability, see instructions and attach form
 Radioactive Drug Research Committee	
• Radioactive Drug Research Committee (RDRC)
 Markey Cancer Center (MCC) Protocol Review and Monitoring Committee (PRMC)	
• Markey Cancer Center (MCC) Protocol Review and Monitoring Committee (PRMC)** - Attach MCC PRMC materials, if any, per instructions.
 Graduate Medical Education Committee (GME)	
• Office of Medical Education (OME)
 Office of Medical Education (OME)	
• Graduate Medical Education Committee (GME)

Attachments

**** If your study involves cancer research, be sure to select "Cancer Research" in the "Research Attributes" section.** ORI will send your research protocol to the Markey Cancer Center (MCC) Protocol Review and Monitoring Committee (PRMC). The [MCC PRMC](#) is responsible for determining whether the study meets the National Cancer Institute (NCI) definition of a clinical trial and for issuing documentation to you (the investigator) which confirms either that PRMC approval has been obtained or that PRMC review is not required. Your IRB application will be processed and reviewed independently from the PRMC review.

ADDITIONAL INFORMATION/MATERIALS**0 unresolved comment(s)**

Do you want specific information inserted into your approval letter? Yes No

Approval Letter Details:

If you wish to have specific language included in your approval letter (e.g., serial #, internal tracking identifier, etc...), type that language in the box below exactly as it should appear in the letter. The text you enter will automatically appear at the top of all approval letters, identical to how you typed it, until you update it. Don't include instructions or questions to ORI staff as those will appear in your approval letter. **If these details need to be changed for any reason, you are responsible for updating the content of this field.**

Additional Materials:

If you have other materials you would like to include for the IRB's consideration, check all that apply and attach the corresponding documents using the Attachments button below.

Detailed protocol
 Dept. of Health & Human Services (DHHS) approved protocol (such as NIH sponsored Cooperative Group Clinical Trial)
 Other Documents

Protocol/Other Attachments

Attach Type	File Name
Other	K202651.pdf

**IF APPLICABLE FOR RELIANCE: I attest that the principal investigator has been notified of the regulatory requirements of both the Reviewing and Relying IRBs, according to the information provided in the E-IRB application. The attached Reliance Assurance Statement, signed by the principal investigator, confirms that he/she can comply with both sets of IRB requirements.

SUBMISSION INFORMATION**0 unresolved
comment(s)**

Each Section/Subsection in the menu on the left must have a checkmark beside it (except this Submission section) indicating the Section/Subsection has been completed. Otherwise your submission for IRB review and approval cannot be sent to the Office of Research Integrity/IRB.

If applicable, remember to update the Approval Letter Details text box under the Additional Information section

If your materials require review at a convened IRB meeting which you will be asked to attend, it will be scheduled on the next available agenda and you will receive a message to notify you of the date.

If you are making a change to an attachment, you need to delete the attachment, upload a highlighted version that contains the changes (use Document Type of "Highlighted Changes"), and a version that contains the changes without any highlights (use the appropriate Document Type for the item(s)). Do **not** delete approved attachments that are still in use.

Your protocol has been submitted.

STATISTICAL METHODS: For the prospective section, a power analysis was conducted based on effect sizes or efficacy of other MAD appliances as previously reported in the literature. Based on the effect sizes of the MAD based on the meta-analyses ($d = -2.063$),(9) we conducted a meta-analysis using GPower which revealed that obtaining a sample size of 33 participants would provide us 80% power to detect the anticipated effects.

Aim 1.1 was to assess the efficacy of the NOA® mandibular advancement device. To do this, we had two different criteria for success as defined before. For each of these criteria, we calculated the proportion of patients who “succeeded” vs. “failed.” As exploratory analyses, we used independent samples t-test or chi-square testes (as appropriate) to compare baseline demographic characteristics between those who succeeded and failed for each of the criteria. **Aim 1.2** was to describe the percentage of advancement (%) needed to reach efficacy for the NOA® appliance in the management of obstructive sleep apnea. For this aim, we only examined the data of those who “succeeded” in Aim 1.1. Paired samples t-tests were carried out to detect the possible statistically significant differences in each of the parameters studied before and after receiving the treatment. The sociodemographic characteristics and other variables of interest of the patients included in the prospective and retrospective studies were described (n, mean \pm SD).

Aim 2 was to describe patient compliance to the NOA® device in the management of obstructive sleep apnea. Using the definition of compliance provided above, we computed the proportion of study participants who complied with the NOA® appliance and described the use in terms of nights per week and hours per night (n, mean \pm SD).

Aim 3 was to assess the incidence and prevalence of temporomandibular disorder (TMD) diagnoses, morning headaches, possible sleep bruxism, nighttime voids, sleep quality, side effects, and of problems related to the NOA® appliance during the titration process by using paired samples t-test or chi-square testes (as appropriate) to compare baseline and final values between those who succeeded and failed for each of the criteria.

Mean and standard deviation and other centralization measures were calculated for quantitative variables, frequencies, and percentage values were calculated for categorical variables. The McNemar test was used as a significance test, with which assessed if there were significant changes. Statistical significance was defined by $p < 0.05$. All analyses were conducted using SPSS version 29.

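### Aim 3 names a paired t-test for a succeeded-versus-failed comparison that it cannot make; Aim 1.2 should also state which patients its before-after tests use

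*Combined protocol and SAP*

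**What the plan says.** All of the analysis wording is in the Statistical Methods section of the combined protocol and SAP.

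- **Aim 1.1** has two success definitions ("To do this, we had two different criteria for success as defined before") and reports the proportion who succeed on each. For an exploratory look at the two resulting groups it says "we used independent samples t-test or chi-square testes (as appropriate) to compare baseline demographic characteristics between those who succeeded and failed".
- **Aim 1.2** describes the percentage of advancement needed: "For this aim, we only examined the data of those who “succeeded” in Aim 1.1". The next sentence reads "Paired samples t-tests were carried out to detect the possible statistically significant differences in each of the parameters studied before and after receiving the treatment". After that comes a general statement: "The sociodemographic characteristics and other variables of interest of the patients included in the prospective and retrospective studies were described".
- **Aim 3** covers TMD diagnoses, morning headaches, possible sleep bruxism, nighttime voids, sleep quality, side effects and appliance problems. Under both criteria, it is to be met "by using paired samples t-test or chi-square testes (as appropriate) to compare baseline and final values between those who succeeded and failed".
- **The closing paragraph** says "frequencies, and percentage values were calculated for categorical variables", and then "The McNemar test was used as a significance test, with which assessed if there were significant changes". No aim or outcome is attached to the McNemar sentence.

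Two other sections bear on this. Research Procedures defines Criterion I as a fall of more than 50% in AHI/RDI, and Criterion II as a final AHI/RDI below 5, or below 15 with symptom improvement. Objectives (item 3) asks for incidence and prevalence of TMD associated with use of the device.

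**The concern.** In Aim 3 the named test and the stated comparison do not match. An analyst who follows the text cannot produce a succeeded-versus-failed result for a numeric outcome. The nearest thing that can be run is a paired test in each group separately. The natural misuse is then to read significance in one group and not in the other as a difference between them. In addition, Objective 3 concerns everyone who uses the device, whereas Aim 3 is framed only by success status and gives no at-risk denominator for new cases.

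In Aim 1.2 the before-after tests come straight after a sentence limiting the data to successes, and no other set is named. If the limit carries over, the AHI/RDI test is run in patients who were selected on AHI/RDI. Two success criteria exist, and the Aim 1.2 sentence does not say that it is applied for each.

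**Working it through.** No figure in the plan depends on this point, so there is none to reproduce. The mismatch in Aim 3 follows from the text; the arithmetic only gives its possible size.

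**1. Tests against questions**

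| Test named | What it compares | Fits succeeded vs failed? | Fits change over time? |
|---|---|---|---|
| Paired t (Aim 3) | same patients, two times | no | yes |
| Chi-square (Aim 3) | different patients, one time | yes, categorical | no |
| Independent t (Aim 1.1, baseline demographics only) | different patients | yes, numeric | no |
| McNemar (no aim given) | same patients, two times, binary | no | yes |

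The choice left open in Aim 3 is between its two named tests, so it does not bring in a two-sample test on change. For numeric outcomes the group comparison has no valid test.

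**2. Outcomes affected**

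Data Collection & Research Materials gives a baseline and a later measurement for morning headaches (rating scale), night-time urination (count) and PSQI. Side effects and appliance problems are recorded at follow-up sessions, with no baseline described. The paired t-test therefore bears on the first three.

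**3. Separate paired tests when the groups do not differ**

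Assumptions (none are in the documents): 45 patients split 30 succeeded and 15 failed; change Normal with SD 1 and the same true mean δ in both groups; two-sided 0.05.

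The power of a paired t-test with n patients is that of a noncentral t with n − 1 degrees of freedom and noncentrality δ√n. With powers p₁ and p₂, the verdicts disagree with probability p₁(1 − p₂) + p₂(1 − p₁).

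- δ = 0.5: noncentralities 0.5√30 = 2.74 and 0.5√15 = 1.94; powers 0.754 and 0.438. Disagreement = 0.754 × 0.562 + 0.438 × 0.246 = 0.424 + 0.108 = 0.53.
- δ = 1.0: noncentralities 5.48 and 3.87; powers 0.9996 and 0.949. Disagreement = 0.9996 × 0.051 + 0.949 × 0.0004 = 0.05.

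Simulation gives 53% at δ = 0.5, and a two-sample test on change is significant in 5%, its nominal level. A 35/10 split gives 0.8195 × 0.7068 + 0.2932 × 0.1805 = 0.63 at δ = 0.5, so the figure depends on the split as well as on δ.

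**4. Aim 1.2, only if the successes-only limit carries over**

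Input from the plan: d = -2.063. Assumptions: log AHI bivariate normal, baseline median 20 per hour, log-SD s from 0.6 to 1.0, correlation r between nights from 0.6 to 0.8. The mean log fall is m = 2.063 × s√(2(1 − r)) if d is a paired standardised change, or m = 2.063 × s if d is in baseline SD units. A Criterion I success has a log fall above ln 2 = 0.693. The ratio reported is the mean fall in successes divided by the mean fall in all patients.

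- Largest case (paired reading, s = 0.6, r = 0.8): SD of change = 0.6 × √0.4 = 0.379; m = 0.783; reduction 1 − e^(−0.783) = 54%; success share Φ((0.783 − 0.693)/0.379) = 59%; ratio 1.33.
- Smallest case (baseline-SD reading, s = 1.0, r = 0.8): m = 2.063; reduction 87%; ratio 1.01.

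Over the whole grid the ratio is 1.10 to 1.33 on the paired reading and 1.01 to 1.13 on the baseline-SD reading. Criterion II selects on the final value, so under it the direction of bias need not be upward.

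**The case against.** **On Aim 3.** The wording may be loose: paired tests within each group for change, and chi-square between groups for categorical items. Several Aim 3 outcomes are categorical, and chi-square is valid for comparing groups on them. The plan nowhere says that it will infer a difference from one significant and one non-significant result. All of this stands, and it limits the reach of the point. It does not repair the numeric comparison, because the text says the comparison is between the groups and names no test for it. A reader might infer that side-effect comparisons are distorted in the same way. The documents do not support that, since no baseline is described for side effects or appliance problems. Nor can it be said that all-user prevalence will go unreported, because the closing paragraph promises frequencies and percentages.

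**On Aim 1.2.** A reader might infer that the plan commits to a circular efficacy test. The text does not show this. The limit to successes is stated for that aim, which is to describe percentage advancement, and that use is legitimate. The following sentences are general, and one covers patients in both the prospective and retrospective parts. The success criteria can also be read as carried over from Aim 1.1, which applies each of them. What remains is that the analysis set is not named.

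**Conclusion.** Aim 3 is wrong as written for its numeric outcomes with a stated baseline. This rests on the text alone. The possible harm is conditional: about 53% discordant verdicts at a common change of 0.5 SD and about 5% at 1.0 SD for a 30/15 split, and only if separate verdicts are compared. The split and the changes are assumptions.

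Aim 1.2 needs a clarification; it is not a demonstrated error. Only the successes-only reading is circular under Criterion I, and at the plan's own effect size the inflation would be about 1.01 to 1.33 times under the assumed log-normal AHI.

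A reader might go further and conclude that the efficacy result is unsound. The documents do not support that: Aim 1.1 reports the proportion who succeed, with failures counted, and does not rest on either test. Severity: minor to should-fix.

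**What to change.** **Aim 3**

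- For succeeded versus failed: a two-sample test on change, or a regression adjusted for baseline, for numeric outcomes; chi-square or Fisher's exact test for categorical ones.
- For change over time: a paired t-test (numeric) or McNemar (binary) in all participants, with the McNemar sentence tied to this aim.
- In line with Objective 3, report TMD prevalence in all device users, and new cases among those free of TMD at baseline.

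**Aim 1.2**

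- State that the AHI/RDI before-after analysis uses all participants with both sleep studies.
- Keep the success subset, separately for each criterion, for describing percentage advancement.

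**Cost.** Wording changes and a little re-analysis of data already planned for collection. The group comparison will have low power if failures are few. Even with an equal split, 80% power at two-sided 0.05 needs a difference of about 1.01 SD with 33 patients in total, or 0.85 SD with 45. If the before-after analysis had been run in Criterion I successes only, the all-participant AHI/RDI reduction may be smaller.

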At the device delivery appointment, we will fabricate an aligner for the patient to wear for 10 minutes each morning after waking and removing the OrthoApnea NOA® oral appliance. The morning aligner (TAP® AM Aligner) is a record of the patient's habitual bite (the way the teeth come together normally) that will reposition their mandible back into its normal position. It is part of the standard of care for patients undergoing mandibular advancement (MAD) therapy. The aligner is constructed from a thermoplastic material that, when heated, can be molded by hand onto the upper or lower teeth. Once the thermoplastic material is molded around the teeth, they will be instructed to bite down while it is still soft. This will create indentations for the opposing teeth and allow them to be set at their 'normal' and proper biting position. After the molded thermoplastic material has hardened at normal temperature, it is removed from the mouth and trimmed, if needed.

Follow up sessions will be scheduled every two weeks until maximum therapeutic benefit is achieved. At each follow up visit patients will be asked to fill out a questionnaire and further advancement of the MAD will be determined by changes in patients' symptoms and Epworth Sleepiness Scale (ESS). Measures of successful management include: ESS < 10, and >70% reduction or absence of snoring, observed apneic events, and daytime fatigue, to be assessed via questionnaire using a numerical rating scale (NRS). Once the patient has obtained successful management of symptoms, 80% of maximum protrusive or is unable to tolerate the advancement, a home sleep apnea test (Alice NightOne, Phillips Respironics®) will be provided to the patient to perform one night while wearing the appliance to determine the efficacy of the MAD. We will verbally instruct the patient how to operate the machine, and a printed copy of the manufacturer protocol for patients will be provided. Additionally, we will provide our contact number if any question arise. An appointment will be scheduled in the following 2-3 days to return the machine, and to further advance the appliance if needed. Sleep parameters including: AHI, RDI, minimum and average oxygen saturation will be extracted from the initial PSG, and by a trained technician from the final home sleep apnea test, which will be scored following the American Academy of Sleep Medicine Scoring Manual.

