The efficacy of the appliance for the management of OSA will be established based on two criteria. Criterion I: > 50% reduction of AHI/RDI. Criterion II: AHI/RDI < 5 events/hour or <15 events/hour with a significant reduction of OSA associates symptoms as defined before. Therapeutic failure will be established when at 100% of advancement of the device, there is less than 50% of reduction of the AHI/RDI with a residual AHI/RDI >5 events/hour with OSA associates symptoms.

If the criteria for success is reached, the participation of the patient in the present study will be ended. The subject will be offered to continue with standard of care in the OFPC for future follow-ups, and a report will be provided and sent to the treating sleep physician. The subject will be allowed to keep the appliance after the study is completed. If participants do not reach a successful management of OSA at 100% of advancement, they will be referred back to their referring sleep physician to consider another treatment option.

The participation in this research will last between seven to sixteen weeks depending on the time for each patient's individual improvement. The initial visit will last 45-60 minutes, and the follow-up sessions will take about 30-45 minutes. After participation in the study is completed, the participants will be allowed to keep the MAD and all the accessories provided by the manufacturer

RETROSPECTIVE SECTION:

Archival data will be extracted from records of patients that started MAD therapy for OSA at the Orofacial Pain Clinic (University of Kentucky) between 01/01/2010 and 08/17/2021. An active study involving MAD therapy outcomes (protocol #46643; same PI, [name] [name]) includes a consent form for the retrospective participants to collect retrospective data and future use of that data in future research projects. The data collection process of the previous study is being conducted using RED Cap (CCTS - University of Kentucky), and through that software, we intend to obtain a report to identify subjects that started MAD therapy and had a second sleep study performed to assess the effectiveness of the MAD. Data regarding demographic characteristics (age, gender, BMI and OSA

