diagnosis), sleep parameters (AHI, RDI, minimum and average oxygen saturation), level of advancement of the MAD (%) prior to the second sleep study, and compliance of use will be extracted creating a deidentified "report" (spreadsheet) from the RED Cap database (assigning progressive numbers (starting with M51)).

Attachments

Data Collection & Research Materials

In this section, please provide the following:

- Describe all sources or methods for obtaining research materials about or from living individuals (such as specimens, records, surveys, interviews, participant observation, etc.), and explain why this information is needed to conduct the study.
- For each source or method described, please list or attach all data to be collected (such as genetic information, interview scripts, survey tools, data collection forms for existing data, etc.).
- If you will conduct a record or chart review, list the beginning and end dates of the records you will view.

This study has a prospective and a retrospective component. (SEE ANNEX IN ATTACHMENTS)

1) Prospective study: data will be obtained using paper questionnaires:

- Demographic information regarding age, race, gender and comorbidities will be extracted from the initial questionnaire (Annex 1).
- The self-reported use of MAD will be assessed at each follow-up via questionnaire on a five-point checklist (number hours per night and nights per week) (to be extracted from Annex 6).
- Epworth sleepiness scale (ESS) (Annex 1 and 6)
- Snoring, observed apneic events, and daytime fatigue, to be assessed via questionnaire using a numerical rating scale (NRS) (to be extracted from Annex 1 and 6).
- Sleep parameters including: AHI, RDI, minimum and average oxygen saturation will be extracted from the initial PSG, and by a trained technician from the final home sleep apnea test.
- The presence of signs, symptoms of TMD will be assessed following the Diagnostic Criteria for Temporomandibular Disorders (DC/TMD) Symptom Questionnaire and Examination Form (Annex 2 and 4).

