- Additional parameters will be controlled, including the presence of morning headaches (to be evaluated via questionnaire at baseline and at each follow-up using NRS), waking up during the night to urinate (to be evaluated at baseline and at each follow-up via questionnaire using continuous numeric scale), and the sleep quality (will be assessed at baseline and when performing the home sleep apnea test, using the Pittsburgh Sleep Quality Index (PSQI) questionnaire). Patients subjective perception of improvement will be assessed at each follow up using visual analog scale (to be extracted from Annex 6).
- Incidence of side effects will be assessed at each follow-up session, including subjective increase/decrease salivation (measured via questionnaire using numeric rating scale), increase/decrease teeth mobility, changes in occlusal contacts (measured in habitual occlusion using 0.01 mm occlusal registration strips (ARTUS corporation®) (to be extracted from Annex 6&7).
- Problems related to the appliance will be measured at each follow up session, considering appliance breaks, cracks, deformation, retention changes, wear, discoloration changes and calculus accumulation (to be extracted from Annex 7).

2) Retrospective study: Archival data will be extracted from records of patients that started MAD therapy for OSA at the Orofacial Pain Clinic (University of Kentucky) between 01/01/2010 and 08/17/2021. An active study involving MAD therapy outcomes (protocol #46643; same PI, [name] [name]) includes a consent form for the retrospective participants to collect retrospective data that allows to use the obtained data in future research projects. The data collection process of the previous study is being conducted using RED Cap (CCTS - University of Kentucky), and through that software, we pretend to obtain a report to identify subjects that started MAD therapy and that had a second sleep study performed to assess the effectiveness of the MAD. Data regarding demographic characteristics (age, gender, BMI and OSA diagnosis), sleep parameters (AHI, RDI, minimum and average oxygen saturation), level of advancement of the MAD (%) prior to the second sleep study, and compliance of use will be extracted creating a deidentified "report" (spreadsheet) from the RED Cap database (assigning progressive numbers (starting with M51)).

Attachments

Attach Type	File Name
DataCollection	Annex MP Orthoapnea.docx

Resources

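### Criterion II sorts some participants by their own symptom ratings, so Aim 3's comparison of other self-reports between Criterion II groups cannot be read as an effect of apnea control

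*Combined protocol and SAP*

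**What the plan says.** The Statistical Methods section lists the Aim 3 outcomes as TMD diagnoses plus "morning headaches, possible sleep bruxism, nighttime voids, sleep quality, side effects, and of problems related to the NOA® appliance". It analyses them with paired t-tests or chi-square tests "to compare baseline and final values between those who succeeded and failed for each of the criteria". It also names McNemar's test and sets significance at p<0.05.

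The two criteria are in Research Procedures, prospective section. The first is "Criterion I: > 50% reduction of AHI/RDI". The second is "AHI/RDI < 5 events/hour or <15 events/hour with a significant reduction of OSA associates symptoms as defined before". The symptom definition it refers back to, earlier in the same section, is "ESS < 10, and >70% reduction or absence of snoring, observed apneic events, and daytime fatigue".

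Data Collection & Research Materials gives the sources. The symptom components are patient ratings: "Snoring, observed apneic events, and daytime fatigue, to be assessed via questionnaire using a numerical rating scale (NRS"). Morning headache is collected in the same way: "presence of morning headaches (to be evaluated via questionnaire at baseline and at each follow-up using NRS"). Nighttime voids come from a questionnaire at baseline and each follow-up. Sleep quality is the PSQI, completed at baseline and at the home sleep test. Study Design describes the prospective part as uncontrolled and open-label.

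**The concern.** A participant whose final AHI/RDI lies from 5 to <15 is placed in the Criterion II success or failure group by his or her own questionnaire answers. Aim 3 then compares other questionnaire answers from the same unblinded person across those groups. Someone who tends to rate everything as better is more likely to be counted a success and also more likely to report better sleep and fewer headaches, whatever happened to the airway.

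A reported result such as better sleep quality among successfully managed patients could then come partly from how the groups were formed. Nothing in the plan separates the symptom part of Criterion II from the AHI/RDI part in this comparison.

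**Working it through.** The plan gives no figure for this comparison, so there is none to reproduce. The check traces the overlap in the text and then asks how large its effect could be.

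**Where symptoms decide the group** (literal reading of Criterion II)

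| Final AHI/RDI | Criterion II result | Decided by |
|---|---|---|
| <5 | success | sleep test |
| 5 to <15 | success only with symptom relief | participant's questionnaire |
| 15 or more | failure | sleep test |

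Criterion I is a sleep-test ratio in every row. Headache, voids and PSQI are not components of either criterion. The link therefore runs only through correlation between self-reports.

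**Size of the difference.** Let a and b be the shares with final AHI/RDI <5 and 5 to <15. Let p be the share meeting the symptom target and r the correlation between the symptom score and the change in the Aim 3 outcome. Take both as normal and unrelated to AHI/RDI, so that any difference is spurious. With z the cut-point for p and φ the normal density:

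- P(success) = a + b·p
- difference in SD = r·b·φ(z) / [P(success) × (1 − P(success))]

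None of a, b, p or r is in the documents. Assume a = 0.30 and b = 0.40.

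| p | φ(z) | P(success) | Difference at r = 0.3 / 0.5 / 0.7 |
|---|---|---|---|
| 50% | 0.399 | 0.30 + 0.40×0.50 = 0.50 | 0.19 / 0.32 / 0.45 |
| 80% | 0.280 | 0.30 + 0.40×0.80 = 0.62 | 0.14 / 0.24 / 0.33 |
| 90% | 0.1755 | 0.30 + 0.40×0.90 = 0.66 | 0.09 / 0.16 / 0.22 |

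For example, at p = 50% and r = 0.5: 0.5 × 0.40 × 0.399 / (0.50 × 0.50) = 0.32 SD.

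**Chance of p<0.05.** This was simulated with a two-sample t-test. The assumptions were: baseline AHI at least 5, median 20 before truncation, log SD 0.7; median reduction 55%, log-ratio SD 0.7. About 43% of simulated participants then fall in the 5 to <15 band. The sample sizes are the 33 in Statistical Methods and the 45 in the study population section. That the plan gives two sizes is a separate matter. Ranges cover r = 0.3 to 0.7, and repeat runs agree to within about 3 percentage points.

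| Meeting symptom target | Grouped by Criterion II | Grouped by AHI/RDI only |
|---|---|---|
| 50% | 10–29% (n=33), 11–36% (n=45) | about 5% |
| 80% | about 7–20% | about 5% |
| 90% | about 5–10% | about 5% |

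**If the planned paired tests are run within each group.** The rates above do not then apply, but the selection still shifts the changes. At p = 50% and r = 0.5 the shift in successes is 0.5 × 0.40 × 0.399 / 0.50 = +0.16 SD, and in failures −0.16 SD.

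**The case against.** The case on the other side has four parts.

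- **The test.** A paired t-test and McNemar's test work within participants. The independent-samples t-test is named only for the Aim 1.1 baseline comparison. This stands: the rejection rates describe one possible reading of an unclear between-group analysis. They are not properties of a test that the plan specifies.
- **The assumptions.** The correlation is assumed, and the device is advanced at follow-up visits according to the same symptoms that form the target, so high attainment is plausible. This also stands. At 90% attainment the inflation is small.
- **The claim.** Aim 3 is worded as incidence and prevalence, and the plan nowhere says that it tests whether apnea control improved headache or sleep. Describing outcomes by a composite definition of success is legitimate. But the plan attaches significance tests at p<0.05, and only the Aim 1.1 baseline comparisons are labelled exploratory, so a reader could easily draw that inference.
- **Criterion I is reported too.** A clean comparison is already planned. That limits the harm but does not repair the Criterion II result beside it.

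A reader might go further and infer that the difference is built in by definition. The documents do not support this, because headache, voids and PSQI are not part of Criterion II. If they were uncorrelated with its symptom items, there would be no spurious difference. Nor is it necessary to drop the Criterion II breakdown.

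**Conclusion.** The concern holds in a limited form. For headache, voids and PSQI, a difference between Criterion II groups cannot by itself be read as evidence that controlling apnea improved them. The overlap follows from the text. Its size does not: about 0.1 to 0.5 SD, and about 5% to 36% rejection against about 5%, rest on an assumed correlation of 0.3 to 0.7, attainment of 50% to 90%, assumed AHI distributions and a two-sample t-test.

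A reader might also take the symptom clause to govern both thresholds of Criterion II. That would enlarge the effect: a separate simulation at n = 45 with 30% to 70% attainment gave 0.29 to 1.03 SD and 16% to 85% rejection. The wording attaches the clause most naturally to the <15 threshold, so those figures are not relied on here.

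Nothing here bears on the Criterion I comparisons, the Aim 1.1 success proportions, or the clinician-assessed and appliance outcomes.

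**What to change.** In the Aim 3 paragraph, for the patient-reported outcomes:

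- Base the success-versus-failure tests and conclusions on Criterion I, or on the AHI/RDI thresholds of Criterion II without the symptom clause.
- Keep the full Criterion II breakdown as description only, without p-values, with a sentence stating that group membership depends partly on the participant's own symptom ratings.
- Name the test that compares successes with failures, since a paired test does not.

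This needs no new data and fewer tests. The small downside is that these outcomes are no longer formally tested by the composite definition of success. The Statistical Methods text is in the past tense. If the analysis has already been run, the relabelling should be disclosed as a change and the Criterion II results kept visible.
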